The proposed study seeks to reduce HIV/AIDS-associated stigma (both internalized and family-level) and its negative impact on children and adolescents (10-14 years). Adolescence is a period of multiple vulnerabilities marked by the onset of physical and emotional maturation accompanied by the challenges of adapting to social, emotional, and cognitive changes.^{38,56} Hence, a young person needs additional support, including emotional support and acceptance from family and community members. Yet, many CLWH cannot count on the “normal” transition to adolescence due to stigma where community and family members ostracize them for being HIV positive,^{55,38,58-62} and where family members suffer the same treatment due to their association with CLWH. Thus, understanding the role of family members, and involving them in the design and implementation of family-level HIV-related programs and interventions for CLWH is essential to their success.

A.4. Multiple Family Groups (MFG) within Communities. Families’ protective roles in influencing children’s behavior and mental health have been well documented.⁶³⁻⁶⁵ Studies have documented that quality of family relationships predicts child mental health functioning and overall adjustment, and that when families are consistently involved in children’s lives, they experience a more positive transition through adolescence.^{66,67} Parental skills have been associated with young people’s psychological adjustment, less risky sexual behavior, and less susceptibility to peer pressure.⁶⁸⁻⁷⁰ Moreover, parent-child communication and involvement may be adversely affected by stigma. Yet, children with more frequent and open communication with parents have been shown to have better psychological adjustment.⁷¹⁻⁷⁵ Therefore, family support strategies, including MFGs, may strengthen the functioning of families, hence addressing individual and family-level stigma.

A.5. Existing HIV Stigma Interventions Primarily Target Non-Infected Populations (NIP). The negative impact of HIV/AIDS-associated stigma has been well-documented. Yet, recent reviews found that stigma

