reduction interventions for CLWH in SSA are almost non-existent.^{34,35} Existing interventions focus on reducing fear of HIV infection among NIP,³⁵ as they interact with PLWH. For example, of 48 stigma reduction interventions, only three aimed to reduce stigma among PLWH in SSA.^{76,77} None targeted CLWH, nor assessed the impact of stigma reduction on HIV-related outcomes.²⁵ This study offers an opportunity to develop a culturally acceptable and effective family-level intervention to address HIV/AIDS-associated stigma and its impact on CLWH's wellbeing in SSA.

members of PLWH are also subjected to and experience stigma via similar mechanisms. Within this framework, MFG provides opportunities for parents and children to communicate in a safe setting. It focuses on addressing internalized and family-level stigma by normalizing shared experiences with other families,⁷⁸ foster peer support and family communication, facilitate optimism and morale, and enhance interpersonal and coping skills.⁷⁸ On the other hand, G-CBT for stigma, addresses internalized stigma through the core components of psychoeducation, cognitive restructuring, and skill-building to increase adaptive coping mechanisms.⁷⁹ These mechanisms may impact a range of psychological, behavioral, and health outcomes for CLWH and their families (Fig. 1).

[figure not shown]
B. INNOVATION

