C.1. Preliminary Studies. This study is informed by findings and lessons learned from the investigative team. **[name] (MPI)** is a new investigator with extensive training and experience conducting research in Uganda among children and adolescents affected by HIV/AIDS. **Drs. [name] and [name] (MPI)** have collaborated on several NIH-funded studies (Suubi-R21MH076475; Suubi-Maka R34MH081763; Bridges-R01HD070727). **[name] (MPI)**, served as the PI on four randomized control trials focused on children affected by HIV/AIDS in Masaka (Suubi-R21MH076475; Suubi-Maka-R34MH081763; Bridges- R01HD070727; Suubi+Adherence R01HD074949). These studies applied principles of MFGs as the delivery platform for the interventions. Study findings indicate improved social, economic, health and mental health outcomes for children and adolescents affected by HIV/AIDS and their caregivers.^{57-62, 85-91} **[name] (Co-I)** has extensive expertise in qualitative research methodologies, including design, data collection, and analysis skills. **[name] (In-country PI)** has extensive expertise in mental health (including CBT intervention) and implementation of community based mental health programs. **Drs. [name] and [name]** are currently implementing a NIMH-funded study (U19MH110001) that examines the implementation, effectiveness and sustainability of an MFG intervention for child behavioral challenges in Uganda, Ghana, and Kenya. **Dr.**

[figure not shown]
A.6. Theoretical Framework. The HIV Stigma Framework³⁶ suggests that HIV stigma impacts PLWH via distinct HIV stigma mechanisms of internalized, anticipated, and enacted HIV stigma. Anticipated and enacted HIV stigma involve experiences with others.^{26,37} Internalized stigma –the focus of this study, involves endorsing negative feelings and beliefs associated with HIV and applying them to the self. Family

[name] (Co-I) has expertise in social exclusion, stigma, and mental health⁹² (see team structure). **[name]** is a biostatistician and consultant on the proposed study who has worked with [name] for over 10 years.

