Treatment Arm 1 (G-CBT): In addition to usual care, children in this arm will receive a 10-session G-CBT for HIV/AIDS-associated stigma. While G-CBT has not been tested in SSA to reduce HIV/AIDS-associated stigma, it has been found effective in reducing self-stigma among adults with mental illness both in the U.S. and other countries.⁹⁷⁻⁹⁹ G-CBT has been widely used and found to be more effective than individual CBT on a range of mental disorders among children,¹⁰⁰⁻¹⁰³ including a potential low-cost alternative to individual therapy in developing countries where access to psychotherapy is scarce due to its high cost.¹⁰⁴⁻¹⁰⁵ G-CBT is likely to offer more opportunities for normalization, positive peer modeling, reinforcements, social support, exposure to social situations and feedback sources, given the context of shared experiences.¹⁰⁶⁻¹¹³ Within G-CBT, for stigma we will utilize core components of CBT (psychoeducation, cognitive restructuring, and skill-building to increase adaptive coping mechanisms):⁷⁹ 1) exploration of HIV's role and impact of stigma in CLWH's life; 2) use of cognitive restructuring to identify and address the negative stigma-associated beliefs, loss of self-worth, self-blame; and 3) skill-building around stress management and emotion-focused coping strategies to address negative feelings (e.g. assertiveness, relaxation skills and problem solving skills).¹¹⁴ CBT typically has a cognitive component which involves helping the person develop the ability to identify and challenge unrealistic negative thoughts, and a behavioral component to promote helpful behavioral responses.¹¹⁴ The research team will ensure: 1) 2) the developmental and cognitive adaptation of the content for children between 10-14 years, and 3) the cultural adaptation of the G-CBT to local context. Content will be tailored to match children's ability to comprehend and implement the therapeutic techniques, including age appropriate activities, child friendly materials, simplified language and visuals (e.g. cartoons),¹¹⁵ less complex behavioral techniques and more support, structure and feedback.¹¹⁶ In addition, the cultural adaptation is intended to enhance its treatment relevance, credibility, efficacy and effectiveness by aligning it to the socioeconomic situation, cultural beliefs, family, political and health systems in the region.¹¹⁷⁻¹¹⁸ G-CBT's cultural adaptation will be ensured by intensive consultative meetings with experienced in-country mental health workers and community leaders, led by in-country PI [name]. G-CBT will be facilitated by trained para-counselors selected using an agreed upon criteria with the community. They will participate in a 5-day training and receive monthly group supervision. Each group will have 10 participants and will last approximately 1 hour. Caregivers will not participate in G-CBT. Sessions will be delivered twice a week, outside of school hours.

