b) *Acceptability.* We will adapt satisfaction surveys, (e.g., the Client Satisfaction Questionnaire (CSQ-8)) to assess acceptability.¹⁶⁰ Items include: "How satisfied were you with the program?", "How helpful was the program in addressing HIV-associated stigma?" and "How likely are you to recommend this program to other families with CLHA?" Given the modest sample size, quantitative analyses of intervention data will be largely descriptive and concentrate on tabulating and summarizing satisfaction outcomes. In regards to hypotheses and methods for primary preliminary/exploratory analyses *to assess study feasibility*, we expect that: **H1:** Following intervention, relative to the control group, participants in both treatment arms (G-CBT and MFG) will have: **H1a:** lower mean count of children reporting HIV/AIDS-associated stigma; **H1b:** lower mean levels of reported HIV/AIDS-associated stigma and improved child psychosocial functioning; **H1c:** lower mean levels of reported child mental health challenges; **H1d:** higher mean levels of adherence. **H2:** Following intervention, relative to the CBT intervention arm, participants in the MFG intervention will have: **H2a:** lower mean count of children reporting HIV/AIDS-associated stigma; **H2b:** lower mean levels of reported HIV/AIDS-associated stigma and improved child psychosocial functioning; **H2c:** lower mean levels of reported child mental health challenges; **H2d:** higher mean levels of adherence. Children will be the unit of analysis for these primary preliminary analyses. We will plot means by group over time to describe overall patterns of change. We will use linear mixed models (LMMs) to evaluate the proposed hypotheses. We will fit LMMs to ensure that all requisite information is available to perform the types of analyses typically undertaken in a formal RCT of intervention efficacy and to obtain valuable effect size information. LMMs will include random intercepts for clinic membership and random intercepts and slopes for subjects (three-level models). Due to the modest sample size, significance testing will be de-emphasized. Similarly, although the modest sample size precludes formal investigation of moderation, we will use the same LMM approach described above to compare children across study arms over time on the moderators listed in Table 1. Additional analyses will consider the role of child gender as a moderator in line with NIH guidelines addressing the importance of sex and gender as critical moderators. These moderation analyses will be secondary exploratory analyses. Additional exploratory analyses will study parents and children jointly as the unit of analysis via dyadic analysis methods such as actor-partner and means-and-deviation models to quantify parent vs. child stigma effects and between- vs. within-dyad effects on mental health outcomes.^{161,162}

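### Do H1a and H2a need one named stigma scale, cut-off and visit before the comparison of MFG with G-CBT can be interpreted?

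*Combined protocol and SAP*

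**What the plan says.** C.3.6 Data Analysis sets two parallel families of hypotheses: H1 compares each treatment arm with control, and H2 compares MFG with G-CBT. H1a and H2a concern a "lower mean count of children reporting HIV/AIDS-associated stigma". H1b and H2b concern "lower mean levels of reported HIV/AIDS-associated stigma and improved child psychosocial functioning". The child is the unit of analysis. Linear mixed models are fitted to all of these, in part "to obtain valuable effect size information", and significance testing is de-emphasised.

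Table 1 lists three child-reported instruments under stigma and shame (a shame questionnaire, a stigma-by-association scale and an HIV stigma mechanism measure), all at baseline, 3 and 6 months. It also lists two caregiver stigma scales.

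On the construct, A.3 says the study "seeks to reduce HIV/AIDS-associated stigma (both internalized and family-level". A.6 names three mechanisms (internalized, anticipated and enacted) and describes internalized stigma as "the focus of this study, involves endorsing negative feelings and beliefs associated with HIV and applying them to the self". On the arms, A.6 says of MFG: "It focuses on addressing internalized and family-level stigma by normalizing shared experiences with other families". It says that "G-CBT for stigma, addresses internalized stigma through the core components of psychoeducation", among other components. C.3.4 adds: "Caregivers will not participate in G-CBT".

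**The concern.** Since H1b and H2b carry the mean level and the child is the unit of analysis, H1a and H2a read most naturally as a yes/no outcome per child. That needs a scale and a threshold, and the available text gives neither. The interventions run for 3 months, so the 3-month and 6-month visits both fall after intervention. Three scales and two visits give 3 × 2 = 6 candidate definitions before any threshold is chosen.

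H2a looks most exposed. If MFG acts on family-level stigma and G-CBT does not, a stigma-by-association score could favour MFG where a score of internalized stigma would not. A.3 and A.6 also seem to disagree on which kind of stigma is meant. At stake would be the effect size carried into a later trial: it could answer a different question from the one intended, or be inflated if scale and threshold were picked once the results were known.

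**Working it through.** **The plan's own figure.** Power Analyses gives detectable differences of .79 to .97 SD with 27 children per group. Inputs from that section are an ICC of .093, alpha .05 and power .80; 9 retained children per clinic follows from 27/3.

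- Design effect: 1 + (9 − 1) × .093 = 1.744.
- Standard error for the mean of two time points: √(2/27 × 1.744 × (1 + r)/2) = .278 at r = .20 and .341 at r = .80.
- Noncentral t with 52 df, two-sided (assumed): .795 and .973, matching the plan. The power text is sound for continuous outcomes; it gives no figure for H1a or H2a.

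**Choice of scale.** Assume normal latent scores, a threshold that flags 50% of untreated children, and an MFG effect of d SD. If G-CBT has a fraction s of that effect on the scale used, the H2a difference is Φ(d) − Φ(s·d).

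| s | d = .79 | d = .30 |
|---|---|---|
| 0 | 28.5 points | 11.8 points |
| .25 | 20.7 | 8.8 |
| .50 | 13.2 | 5.8 |
| .75 | 6.2 | 2.9 |
| 1 | 0 | 0 |

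The striking contrast, 0 on an internalized scale against 28.5 on a family-level scale, takes s = 1 for the first and s = 0 for the second. Neither value is in the plan. H2b predicts lower stigma with MFG, and C.3.4 expects caregiver involvement to improve child outcomes, stigma included. If s on the internalized scale were .75 or .50, the 0 would become 6.2 or 13.2 points. The contrast also presumes that one child scale scores internalized stigma and another family-level stigma; the documents give only their names.

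**Choice of threshold.** For a fixed shift of .79 SD and untreated prevalence p, put z = Φ⁻¹(1 − p) and q = 1 − Φ(z + .79). Then p − q is 17.8, 28.5, 29.6 and 21.2 points at p = 25, 50, 75 and 90%. The sample size per arm for 80% power before clustering, 7.85 × [p(1 − p) + q(1 − q)]/(p − q)², is about 63, 40, 39 and 53. Any dichotomised score behaves this way, so a later trial would have to choose its own threshold in any case.

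**Choice after seeing the data.** This was simulated with no true effect: two arms of 3 clinics × 9 children, ICC .093, three scales correlated .3 to .7, thresholds at 25, 50 and 75% prevalence, and 20,000 runs per setting. Outcomes were analysed at follow-up or as change from baseline; for change, a stable child share of .5 was assumed.

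| Rule | Mean apparent benefit | Benefit of 15 points or more |
|---|---|---|
| One definition fixed beforehand | 0 | 13–16% of runs |
| Best of 3 scales | 9–12 points | 29–37% |
| Best of 3 scales × 3 thresholds | 15–19 points | 43–57% |

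This is a worst case. It describes analysts who search for the best result and report only that one.

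**Precision.** The effective number per arm is 27/1.744 = 15.5. The 95% half-width for a difference, 1.96 × √(2p(1 − p)/15.5), is 35 points at p = 50% and 21 points at p = 90%. The s = 0 difference of 28.5 points, computed at p = 50%, lies inside the 35-point half-width that applies there.

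**A.3 beside A.6.** The A.6 paragraph is split by the page layout. Rejoined, it picks one mechanism out of three and then goes on to say that family members experience stigma through similar mechanisms. A.3 says whose stigma is targeted, the child's own and the family's. One passage concerns mechanism and the other level, so both can be true.

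**The case for a change.** The best case for a change is that C.3.6 calls these primary preliminary analyses and fits the models for effect sizes. Selection after the fact inflates an effect size whether or not a p-value is quoted. Table 1 offers three scales and links none to H1a or H2a. MFG's extra target means the choice of scale partly decides what H2a asks. Naming a scale, threshold and visit would take one sentence and no new data.

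Two parts of this stand: the available text has no rule for reporting stigma, and the H2a estimate can differ between scales. The rest does not carry a change. No passage says that one scale or threshold will be picked from the results. Settling on one visit is not essential, because the mixed model uses repeated measures with subject slopes and group means are plotted over time. Giving one scale headline status before the pilot has shown how the three behave is a preference, and a threshold taken from pooled baseline scores would be a sample quantile without clinical meaning. Family stigma also has its own place in the plan, through the caregiver scales and the exploratory dyadic models. A linear mixed model on a 0/1 outcome estimates a risk difference, so the model does not supply a separate reason to amend.

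**Conclusion.** No change to the plan follows. H1a and H2a lack a written scoring rule in the text available, and one may sit in the incomplete measures text around Table 1. This is the kind of gap analysts fill sensibly: score each child scale by a stated rule and show all three at both post-baseline visits. That removes the selection behind the 9 to 19 point figures.

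The claim that the MFG against G-CBT answer depends on the scale is too strong. It can depend on it, but the documents do not show that it does. The 0 against 28.5 contrast rests on equal effects on internalized stigma, no carry-over of G-CBT to family-level stigma, 50% prevalence, and a reading of the scales from their names. The apparent conflict between A.3 and A.6 disappears when the A.6 paragraph is read whole. The practical consequence is small, because the analysis is exploratory, largely descriptive, and precise only to about 21 to 35 points either way. Confidence is moderate, since part of the measures text could not be read.

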C.2. Study Overview. *Suubi4Stigma*, a mixed-methods sequential explanatory study,⁹³ will address the urgent need for theoretically and empirically informed interventions that seek to reduce HIV/AIDS-associated stigma and its negative impact on child health and psychosocial well-being. We will test the feasibility, acceptability and preliminary effects of the G-CBT versus MFG intervention, two evidence-based interventions that have, to date, been extensively used to address mental health functioning among children and adolescents. Specifically, clinics will be randomized to one of three study arms (see C.3). The conceptual model (Fig 1) specifies the expected relationship between the intervention arms, mechanisms and potential outcomes.

Figure 2. *Suubi4Stigma* Assessment

usual (n=3 clinics; 30 child-caregiver dyads); 2) G-CBT intervention + usual care (n=3 clinics; 30 child-caregiver dyads); and 3) MFG intervention + usual care (n=3 clinics; 30 child-caregiver dyads). Both treatment and control arms will be delivered over a 3-month period. Data will be collected at baseline (pre-intervention), 3-months and 6-months post-intervention initiation. Children in the same clinic will be assigned to the same study condition to avoid contamination (Fig.2).

C.3.1 Study Inclusion/Exclusion Criteria: *Inclusion criteria for children:* The target population for this study is CLWH enrolled in care at a health clinic that has partnered with ICHAD ([name] et al.; *Suubi+Adherence* study). Child inclusion criteria are: 1) HIV+ status- defined as a child tested with confirmation by medical report and has been disclosed to; 2) prescribed ART; 3) living within a family (defined broadly - not necessarily with biological parents); and 4) ages 10 to 14. All eligible CLWH from a particular household will be enrolled in the study and will be assigned to the same study condition. *Inclusion criteria for parents/caregiving families.* Caregivers of CLWH who agree to participate in the study. *Exclusion criteria* includes a significant cognitive impairment of the child or parent that interferes with understanding the informed consent process. *Inclusion criteria for clinics.* Clinics registered and supported by the government to provide ART to CLWH in Masaka.

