
Power Analyses. Although the study purpose is to determine preliminary feasibility and acceptability, rather than conduct formal hypothesis tests, we conducted several power analyses using NCSS PASS to supply additional information. Our power analyses assume $\alpha=.05$, power=.80, 81 participants retained at the final time point following 10% estimated attrition, and a clinic-based conservative unconditional ICC of 9.3% based on our previous SUUBI study of mental health in Uganda children.¹⁶³ For the target enrollment proportion of 70% to assess feasibility, the width to the limit of the confidence interval is 27.9% (standardized distance: .32). For continuous standard normal variables to assess acceptability (e.g., CSQ-8), the distance from the mean to the confidence limit is .30. These distances to confidence limits are between small (.20) and medium (.50) effect sizes. For preliminary efficacy exploratory analyses with two time points and paired comparisons of two out of the three groups at 81/3=27 participants per group (N=54 per comparison), minimum detectable standardized mean differences for continuous outcomes ranged from .79 to .97 for within-subjects correlations r ranging from .20 to .80. In sum, our study is powered to detect small-medium distances to confidence limits for descriptive statistics and large longitudinal analysis effects, though hypothesis testing is not the study focus.

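### The plan gives the mixed model's random effects but not its fixed effects, target contrast or use of baseline; a common-baseline model would give tighter arm differences than the change contrast it implies

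*Combined protocol and SAP*

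**What the plan says.** The analysis of H1 and H2 is in C.3.6 Data Analysis, Aim 1: "We will use linear mixed models (LMMs) to evaluate the proposed hypotheses". The only model terms listed are a random intercept for clinic and a random intercept and slope for each child. No arm, time or arm-by-time term is given, nor a baseline covariate, nor a constraint on baseline means. The hypotheses are worded as mean levels after the intervention. The same section plans plots of arm means over time and, for the moderators, a comparison of arms over time with the same kind of model.

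The design section (C.3) gives the schedule: "Data will be collected at baseline (pre-intervention), 3-months and 6-months post-intervention initiation". Table 1 lists the stigma, psychosocial and mental health scales at all three visits.

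The Power Analyses paragraph describes "preliminary efficacy exploratory analyses with two time points and paired comparisons of two out of the three groups", with "81/3=27 participants per group (N=54 per comparison", and detectable standardized differences that "ranged from .79 to .97 for within-subjects correlations r ranging from .20 to .80".

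The plan de-emphasizes significance testing but says the models are there to supply effect sizes.

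**The concern.** Which effect size the pilot reports depends on a choice the plan leaves open.

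- **Follow-up means only, or means averaged over visits.** A chance baseline difference between arms passes into the estimate to the extent that it persists. With three clinics per arm such differences are not small.
- **Arm-by-time change with free baseline means.** The whole baseline difference is subtracted although only part of it would have persisted. This over-corrects and costs precision.
- **Conditioning on baseline.** Only the persisting part is removed, and the standard error is the smallest of the three in every case computed.

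The options can give different effect sizes from the same data. If none is named in advance, the choice can be made after the data are seen.

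**Working it through.** **Inputs.** Power Analyses paragraph: "Our power analyses assume $\alpha=.05$, power=.80" (taken as two-sided); "81 participants retained at the final time point following 10% estimated attrition"; "a clinic-based conservative unconditional ICC of 9.3" per cent; r from .20 to .80. Design section: 3 clinics and 30 children per arm, so 10 enrolled and 9 retained per clinic. Assumed: outcome variance 1 and the same r between every pair of visits.

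**1. The plan's own figure.** For 27 per arm, two-sided .05, power .80 and 52 df (noncentral t), the detectable difference without clustering is .777. The design effect is 1 + 8 × .093 = 1.744. For the average of two time points the variance factor is (1 + r)/2:
- r = .2: .777 × sqrt(1.744 × .6) = .795
- r = .8: .777 × sqrt(1.744 × .9) = .973

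This matches .79 to .97. The figure rises with r. A change contrast, factor 2(1 − r), would fall from 1.298 to .649. A single follow-up adjusted for baseline, factor 1 − r², would fall from 1.005 to .616. So the power calculation takes no credit for baseline.

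**2. Size of chance baseline differences.** With 10 per clinic the design effect is 1 + 9 × .093 = 1.837. The SD of the baseline difference between two arms is sqrt(2 × 1.837/30) = .35, with a 95% range of about ±.69. The chance that it exceeds .3 SD in either direction is 39%.

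**3. Which reading fits the stated model.** With months 3 and 6 only, each child supplies two variances and one covariance: three quantities for four parameters (intercept variance, slope variance, their covariance, residual variance). The random slope is then not identified, so baseline must be an outcome row. With complete data at 0, 3 and 6 months, a least-squares linear slope is (month 6 − baseline)/6 per month, which is again a change contrast.

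**4. Precision under the stated clinic intercept.** Take 9 children per clinic and a clinic effect constant over time.
- Variance of an arm difference at one visit: V = (2/3)(.093 + .907/9) = .1292, SE .359.
- Covariance between baseline and month 6: K = (2/3)(.093 + (r − .093)/9).
- Share of a baseline difference expected to persist: ρ = K/V.
- Change: variance 2V(1 − ρ). Conditioned on baseline: V(1 − ρ²). Ratio: (1 + ρ)/2.

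| r | ρ | SE follow-up only | SE change | SE conditioned | Variance cut vs change | Interval narrower |
|---|---|---|---|---|---|---|
| .2 | .541 | .359 | .344 | .302 | 23% | 12% |
| .5 | .713 | .359 | .272 | .252 | 14% | 7% |
| .8 | .885 | .359 | .172 | .167 | 6% | 3% |

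For a one-SD baseline difference (.359 in the retained sample), a follow-up contrast is expected to carry .359ρ = .19, .26 and .32. A change contrast over-corrects by .359(1 − ρ) = .16, .10 and .04.

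**5. If clinic effects drift over time** (not in the documents). With an assumed clinic autocorrelation of .5, ρ is .328, .500 and .672, and the variance cut against change is 1 − (1 + ρ)/2 = 34%, 25% and 16%.

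**6. Degrees of freedom.** A common baseline mean or a child-level covariate spends no between-clinic df. A clinic-mean covariate would spend one: of 6 in a three-arm model (critical t 2.447 to 2.571, +5%) or of 4 in a pairwise model (2.776 to 3.182, +15%).

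**The case against.** The strongest defence is that this is a feasibility pilot. An arm-by-time mixed model already uses baseline, and choosing between change and a common baseline mean is a modest matter of efficiency. Much of that stands. Four stronger readings are tempting, and the documents do not support them.

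- **A reader might infer that the plan rejects baseline adjustment.** It is silent, and equally silent on arm and time terms.
- **A reader might infer that baseline goes unused, or that imbalance necessarily passes into the arm contrasts.** The random slope and the wording about arms over time point to a change contrast, which subtracts the imbalance. The detectable differences do match an average that takes no credit for baseline, but they are offered as additional information and do not define the model.
- **A reader might expect a variance gain of 40% to 10% over change**, from (1 + r)/2 at the child level. That requires the clinic-level correlation to equal the child-level one. The plan's clinic intercept is constant over time and cancels in change, which leaves 23% to 6%.
- **A reader might think that adjustment is free and complete.** It removes only what baseline predicts. A common baseline mean assumes comparable arms, and the plan does not say whether recruitment precedes clinic allocation. The covariate version leaves two rows per child, too few for the planned random slope.

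What the defence does not answer is that effect sizes are the stated reason for fitting these models, and the contrast that defines them is not given.

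**Conclusion.** The point holds as a gap in specification with a better model available. Under the plan's own clinic structure the gain over a change contrast is moderate at r = .2 (intervals about 12% narrower) and small at r = .8 (about 3%). It is larger if clinic effects vary over time, which is an assumption. Against a follow-up or time-averaged contrast, the issue is also that chance baseline differences with an SD of about .35 would enter the effect size to the extent that they persist. The figures rest on 9 children retained per clinic, equal variances and equal correlation across visits, known variance components and the stated ICC. They concern continuous outcomes measured at baseline. They do not cover the counts in H1a and H2a, or the pill-count and pharmacy adherence data that Table 1 marks as ongoing. This should be changed, but it does not threaten the feasibility aims.

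**What to change.** In C.3.6, Aim 1, state for the continuous outcomes measured at baseline:

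1. Baseline, month 3 and month 6 are fitted together, with arm-by-visit fixed effects, one common baseline mean for all arms and the planned random effects.
2. The target contrasts for H1 and H2 are the arm differences at month 3 and at month 6, reported with intervals using small-sample degrees of freedom (for example Kenward-Roger).
3. If children are recruited after their clinic's allocation, the model with free baseline means is shown as a sensitivity analysis. The plan should say which comes first.

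An acceptable alternative is the child's own baseline score as an individual-level covariate, with the random slope dropped because two follow-up rows per child cannot identify it. A clinic-mean baseline covariate is best avoided, since it uses a between-clinic degree of freedom.

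The cost is wording. The baseline, month-3 and month-6 assessments are already scheduled, so no visit, measure or participant is added.
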